## DOCUMENT HISTORY

Document	Date of Issue	Summary of Change
Revised Protocol 03	13-Jan-2016	Incorporates Amendment 04
Amendment 04	13-Jan-2016	This amendment changes DLT, dose delay, dose modification and dose discontinuation criteria to align with nivolumab program standard language. Additional changes have been made to platelet inclusion criteria and prohibited medications. Chest x-rays were added to monitor for pulmonary toxicity. Administrative edits and clarifications are also incorporated.
Revised Protocol 02	16-Sep-2015	Incorporates Amendment 03
Amendment 03	16-Sep-2015	This amendment changes dose delay, dose modification, discontinuation and dose limiting toxicity (DLT) criteria to account for the known toxicity profiles of ulocuplumab and nivolumab and correct internal inconsistencies in the management of toxicity. The major change is to remove the requirement to discontinue study therapy for grade 3 platelets > 7 days and replace it with the recommendation to hold study therapy for grade 3 platelets > 7 days.
Revised Protocol 01	20-May-2015	Incorporates Amendment 02
Amendment 02	20-May-2015	This amendment adds a sentinel 400 mg weekly ulocuplumab dose level in the dose evaluation phase at the request of regulatory authorities. It also incorporates administrative edits and minor clarifications to the study procedures.  This amendment applies to all subjects and is to be implemented after IRB/IEC/HA review.
Original Protocol	23-Mar-2015	Not applicable

## SYNOPSIS

### Clinical Protocol CA212115

**Protocol Title:** A Phase 1/2 Study of the Safety and Efficacy of Ulocuplumab Combined with Nivolumab in Subjects with Advanced or Metastatic Solid Tumors

**Investigational Product(s), Dose and Mode of Administration, Duration of Treatment with Investigational Product(s):**

- Ulocuplumab 200 mg, 400 mg, 800 mg or 1600 mg administered IV over 60 minutes every week combined with nivolumab administered IV over 60 minutes at 3 mg/kg every 2 weeks until progression
- Ulocuplumab 1600 mg administered IV over 60 minutes every 2 weeks combined with nivolumab administered IV over 60 minutes at 3 mg/kg every 2 weeks until progression

**Study Phase:** 1/2

**Research Hypothesis:** Treatment with ulocuplumab plus nivolumab will be safe, tolerable and demonstrate a clinically meaningful efficacy in subjects with advanced or metastatic solid tumors.

**Objectives:**

**Primary Objective:**

- Stage 1: To identify the recommended dose and schedule of ulocuplumab, based on safety and efficacy, in combination with nivolumab in subjects with advanced or metastatic tumors
- Stage 2: To evaluate the efficacy, separately by tumor type, based on objective response rate (ORR) or overall survival (OS; randomized Phase 2 study in pancreatic adenocarcinoma (PAC) only), of ulocuplumab combined with nivolumab in subjects with advanced or metastatic tumors

**Secondary Objectives:**

- To assess the safety and tolerability of ulocuplumab combined with nivolumab, in subjects with advanced or metastatic tumors
- To assess progression-free survival (PFS) with ulocuplumab combined with nivolumab, separately by tumor type, in subjects with advanced or metastatic tumors

[figure not shown]
**Exploratory Objectives:**

- [REDACTED]
- [REDACTED]
- [REDACTED]
- [REDACTED]
- [REDACTED]
- [REDACTED]
- [REDACTED]
- [REDACTED]

**Study Design:** This is an open-label, multicenter phase 1/2 study to evaluate safety and efficacy of ulocuplumab in combination with nivolumab in subjects with small cell lung cancer (SCLC) and PAC. The study design allows for the testing of different doses and schedules of ulocuplumab in the Dose Evaluation Phase. In addition, the protocol

[figure not shown]
incorporates a flexible design to permit the initiation of a randomized Phase 2 study with comparative arm in the Dose Expansion Phase if high efficacy is observed. If high efficacy is not observed, the study continues as a single arm study for the Dose Expansion Phase.

**Dose Evaluation Phase (Stage 1)**

[figure not shown]

**Dose Expansion Phase (Stage 2)**

Simon 2-stage (per tumor type):

Randomized Phase 2 (per tumor type):

**Study Population:** Subjects with pathologically confirmed locally advanced or metastatic SCLC and PAC that have failed at least one prior line of chemotherapy are eligible. Subjects must have an ECOG score of 0-1. Subjects with active brain metastases are excluded.

**Study Drug:**

Study Drug for CA212115		
Medication	Potency	IP/Non-IP
Ulocuplumab (BMS-936564)	100 mg (10 mg/mL)	IP
Nivolumab (BMS-936558)	100 mg (10 mg/mL)	IP

**Study Assessments:** Radiographic tumor assessments will be performed at baseline, at 6 weeks from first dose and continue every 6 weeks for the first 24 weeks and every 12 weeks thereafter until disease progression or treatment discontinuation.

**Statistical Considerations:**

**Sample Size:** The sample size will start at dose level 1 (DL1) with a minimum of 3 treated subjects with either PAC or SCLC using a Rolling Six design for evaluation of dose limiting toxicity (DLT). Then, the sample size will be increased by the number of subjects separately by tumor type needed to continue the DLT evaluation at each dose level followed by the number of subjects separately by tumor type needed for one or three randomized cohort(s) to complete the Dose Evaluation Phase. Finally, the sample size will be increased by the number of subjects needed for the Dose Expansion Phase selected for each tumor type.

For SCLC, up to approximately 175 treated subjects may be needed. This sample size considers 3-18 subjects for the DLT evaluation and 19 subjects per cohort (57 subjects for three randomized cohorts) of the Dose Evaluation Phase. The Dose Expansion Phase in the form of a second stage of a Simon 2-stage like design would require an additional 25 subjects OR in the form of a randomized Phase 2 study with a comparative arm would require an additional 50 subjects per arm (ie. 100 subjects for the two arms).

For PAC, up to approximately 331 treated subjects may be needed. This sample size considers 3-18 subjects for the DLT evaluation and 21 subjects per cohort (63 subjects for three randomized cohorts) for the Dose Evaluation Phase. The Dose Expansion Phase in the form of a second stage of a Simon 2-stage like design would require an additional 20 subjects OR in the form of a randomized Phase 2 study with a comparative arm would require an additional 125 subjects per arm (ie. 250 subjects for the two arms).

**Endpoints:** The primary efficacy endpoint will be ORR, as determined by the investigators, for the Dose Evaluation Phase and if a Simon 2-stage like design is continued for the Dose Expansion Phase. If a randomized Phase 2 study with a comparative arm is selected for the Dose Expansion Phase, the primary efficacy endpoint will be ORR for SCLC and OS for PAC. Secondary efficacy endpoints will consist of safety, tolerability and PFS. Safety and tolerability endpoints will consist of the incidence of DLT (primary safety endpoint during the DLT evaluation phase), adverse events (AE), serious adverse events (SAE) and specific laboratory abnormalities (worst grade). Toxicities will be graded using the National Cancer Institute (NCI) Common Terminology Criteria for Adverse Events (CTCAE) version 4.0

**Analyses:** All analyses will be presented separately by tumor type. Within a tumor type, the Dose Evaluation Phase analyses will be presented by cohort. If a Simon 2-stage like design is completed, analyses of the Dose Evaluation Phase and the Dose Expansion Phase will be pooled and presented by cohort. If a randomized Phase 2 study with comparator arm is initiated, the analyses of this design will be presented by treatment arm.

Baseline characteristics and efficacy analyses will be summarized for the All Dose Evaluation Randomized Treated Subjects (primary population) and the All Treated Subjects population by cohort (and, if a randomized two-arm Phase 2 study is initiated, for the All Dose Expansion Randomized Subjects population by randomized treatment arm). ORR will be summarized by a binomial response rate and corresponding two-sided 95% exact CI using the Clopper and Pearson method. If a randomized Phase 2 study is initiated, ORR will be compared between the treatment arms using a one-sided alpha level of 0.10 with Cochran-Mantel-Haenszel (CMH) test stratified by the stratification factors defined for each tumor type. The primary analysis of OS as primary endpoint for PAC will be a comparison of the OS of subjects randomized to ulocuplumab plus nivolumab to that of subjects randomized to the investigator's choice chemotherapy using a one-sided alpha level of 0.10 log-rank test stratified by the stratification factors defined for each tumor type. PFS and OS will be summarized using the Kaplan-Meier (KM) product-limit method.

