**Table 3.1.2-1: Stage 1 Efficacy Threshold For Each Tumor Type**

Efficacy Threshold	SCLC	PAC
Low	≤ 3 responders / 19 subjects	≤ 1 responders / 21 subjects
Moderate	4-8 responders / 19 subjects	2-5 responders / 21 subjects
High	≥ 9 responders / 19 subjects	≥ 6 responders / 21 subjects

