#### **8.4.2.1 Primary Endpoint Methods**

ORR will be summarized by a binomial response rate and corresponding two-sided 90% exact CI using the Clopper and Pearson method. If a randomized Phase 2 study with comparative arm is initiated, ORR will be compared between the treatment arms using a one-sided alpha level of 0.10 with Cochran-Mantel-Haenszel (CMH) test stratified by the stratification factors defined for each tumor type. A two-sided, 80% CI for the difference in response rates will also be computed, adjusting for the stratification factors.

The primary analysis of OS as primary endpoint for PAC will be a comparison of the OS of subjects randomized to ulocuplumab plus nivolumab to that of subjects randomized to the investigator's choice chemotherapy using a one-sided alpha level of 0.10 log-rank test stratified by the stratification factors defined for each tumor type. The hazard ratio and associated two-sided 80% confidence interval will be computed using an univariate Cox proportional hazards model with treatment as the sole covariate. Further analyses of OS will be summarized descriptively using Kaplan-Meier methodology. Median values of OS, along with two-sided 95% CIs using the Brookmeyer and Crowley method considering a log-log transformation, will be calculated. OS rates at 3, 6, 9, 12, 18 and 24 months will be estimated as well as associated two-sided 95% CIs considering a log-log transformation.

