#### **8.5 Interim Analyses**

Within each tumor type, an interim analysis (IA) will be conducted when all subjects in the Dose Evaluation Phase have a minimum of 3 months of treatment or discontinued prematurely. The objectives of this IA will be: 1) to determine if further study of ulocuplumab combined with nivolumab is warranted in the tumor type; 2) if further study is warranted, to select a recommended dose for the Dose Expansion Phase; and 3) if the Dose Expansion Phase is to be completed, to determine whether to conduct a single arm second stage of a Simon optimal 2 stage like design or an open label randomized Phase 2 design with a comparative arm.

The decision to further study ulocuplumab combined with nivolumab in each tumor type will primarily be based on the pre-defined Simon 2-stage design thresholds for the Dose Evaluation Phase (at least 4 responders for SCLC and at least 2 responders for PAC). In addition, the selection of the recommended dose will be based on all available safety and efficacy data for that IA from both tumor types. The decision to proceed from the Dose Evaluation Phase to the Dose Expansion Phase will be conducted for each tumor type independently. Consideration may be given to evaluating final data before decision is reached to stop further study the combination to ensure the full characterization of the response pattern is evaluated.

The decision to proceed with an open label randomized two-arm Phase 2 design rather than completing the second stage of a Simon optimal 2-stage like design for the Expansion Phase will be taken if, among the treated subjects in the recommended dose selected during the Dose Evaluation Phase, a “high” frequency of responders is observed. For SCLC, this “high” number will be at least 9 responders and, for PAC, at least 6 responders.

This number of responders has been defined considering clinical input but, ensuring that the related proportion of responders also presents with a 90% exact CI lower limit above 25% for SCLC or above 12% for PAC. These percentages correspond to the minimum proportion of responders that would be needed at the end of a Simon 2-stage design in order to further evaluate

the drug (for SCLC, 11 responders among the 44 subjects is 25% and, for PAC, 5 responders among the 41 subjects is 12%).

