7 STATISTICAL ANALYSES

7.1 General Methods

All analyses will be presented separately by tumor type.

Descriptive summaries of continuous and other numeric variables will at least consist of the following summary statistics: median, minimum and maximum values. Categorical variables will be summarized by the frequency and proportion of subjects falling into each category. Unless otherwise indicated, percentages in tables will be column percentages, using the total number of observations in the population, grouped by cohort, as the denominator. Percentages will be rounded to one decimal place, and thus may not always add up to exactly 100%.

AEs will be coded using the Medical Dictionary for Regulatory Activities (MedDRA), and the most recent version of the dictionary at the time of the database lock will be used. AEs and laboratory tests will be graded using the National Cancer Institute - Common Toxicity Criteria for Adverse Event (NCI-CTCAE) Version 4.03. Clinical laboratory values will be first reported in using International System of Units (SI). Analyses will be repeated using US conventional units. Medications will be coded using the most recent version of the BMS WHO Drug Dictionary.

Time-to event variables (e.g., PFS, OS, DOR, etc.) will be analyzed using the Kaplan-Meier product limit method (KM). When specified, the median will be reported along with 95% confidence interval (CI) using Brookmeyer and Crowley methodology⁴ (using the log-log transformation for construction of CI). Rates at fixed timepoints (e.g., PFS at 6 months) will be derived from the Kaplan-Meier estimate along with their corresponding log-log transformed CIs. Exact confidence intervals for binomial proportions will be derived using the Clopper-Pearson method⁵.

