7.5.1 Objective Response Rate

BOR will be summarized by response category and ORR will be computed along with an exact 90% CI (primary analysis for ORR as primary endpoint, see [Section 4](#)).

The primary population for estimating the ORR will be the All Dose Evaluation Excluding DLT Treated Subjects population. Additionally, the parameters will be summarized using the All Dose Evaluation Treated Subjects population (supportive analyses). All analyses will be presented as-treated.

For the Dose Evaluation Phase, the decision to further study ulocuplumab combined with nivolumab in each tumor type will primarily be based on the pre-defined Simon 2-stage design thresholds (at least 4 responders for SCLC and at least 2 responders for PAC), using data from the IA. In addition, the selection of the recommended dose will be based on all available safety and efficacy data from both tumor types. The decision to proceed from the Dose Evaluation Phase to the Dose Expansion Phase will be conducted for each tumor type independently. Consideration may be given for evaluating final data before decision is reached to stop further study of the combination to ensure that the full characterization of the response pattern is evaluated.

The decision to proceed with an open label randomized two-arm Phase 2 design rather than completing the second stage of a Simon 2-stage design for the Expansion Phase will be taken if, among the treated subjects in the recommended dose selected during the Dose Evaluation Phase, a “high” frequency of responders is observed. For SCLC, this “high” number will be at least 9 responders and, for PAC, at least 6 responders. This number of responders has been defined considering clinical input but, ensuring that the related proportion of responders also presents with a 90% exact CI lower limit above 25% for SCLC or above 12% for PAC. These percentages correspond to the minimum proportion of responders that would be needed at the end of a Simon 2-stage design in order to further evaluate the drug (for SCLC, 11 responders among the 44 subjects is 25% and, for PAC, 5 responders among the 41 subjects is 12%).

For the Dose Expansion Phase, the primary population will be the All 2-stage Treated Subjects population (as-treated analyses).

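### Does the 95% interval for ORR in the Synopsis, against 90% elsewhere, undermine the primary analysis or the high-efficacy cut-offs?

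*Protocol*

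**What the plan says.** Four places bear on the confidence level for ORR.

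- Protocol Synopsis, Statistical Considerations, Analyses: "ORR will be summarized by a binomial response rate and corresponding two-sided 95% exact CI using the Clopper and Pearson method".
- Protocol Section 8.4.2.1: "ORR will be summarized by a binomial response rate and corresponding two-sided 90% exact CI using the Clopper and Pearson method".
- Protocol Section 8.5, where the high-efficacy counts are explained: the observed proportion "presents with a 90% exact CI lower limit above 25% for SCLC or above 12% for PAC". SAP Section 7.5.1 repeats this explanation.
- SAP Section 7.5.1: "BOR will be summarized by response category and ORR will be computed along with an exact 90% CI". The SAP labels this the primary analysis where ORR is the primary endpoint. SAP Section 7.1 supplies the method: "Exact confidence intervals for binomial proportions will be derived using the Clopper-Pearson method".

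The trigger for the randomised Phase 2 is stated as a count. Protocol Table 3.1.2-1 gives "≥ 9 responders / 19 subjects" for SCLC and the corresponding 6 of 21 for PAC. Section 8.5 says that the high "number will be at least 9 responders and, for PAC, at least 6 responders".

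**The concern.** Two versions of one sentence about the primary endpoint stand in the current protocol, and only the confidence level differs. Nothing presents the 95% interval as a separate or supportive analysis. With two levels in the text, someone could choose between them after seeing the data.

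The level also appears to carry weight in the design. Section 8.5 defends 9/19 and 6/21 by a lower confidence limit above 25% and 12%. A reader who checks those cut-offs with the Synopsis interval finds that both fail. If the cut-offs were re-derived at 95%, they would rise by one responder in each tumour type, and a randomised study would open less often. That study needs 100 subjects in SCLC or 250 in PAC, so the matter looks more than editorial.

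**Working it through.** **Inputs.** The cut-offs are 9/19 and 6/21 (Protocol Table 3.1.2-1). The benchmarks are 25% and 12%, which Section 8.5 derives from the Simon success boundaries: 11/44 = 25.0% and 5/41 = 12.2%. The two levels are 90% (Sections 8.4.2.1 and 8.5, SAP 7.5.1) and 95% (Synopsis). The Simon designs are in Sections 8.1.1 and 8.1.2.

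**Formula.** For x responders among n subjects and two-sided level 1 − a, the Clopper-Pearson lower limit is the a/2 quantile of Beta(x, n − x + 1). The upper limit is the 1 − a/2 quantile of Beta(x + 1, n − x).

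**The plan's own figure.** At 90% (a = 0.10):

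| Observed | 90% exact interval | Benchmark | Met? |
|---|---|---|---|
| 9/19 = 47.4% | 27.4% to 68.0% | 25% | yes |
| 8/19 = 42.1% | 23.0% to 63.2% | 25% | no |
| 6/21 = 28.6% | 13.2% to 48.7% | 12% | yes |
| 5/21 = 23.8% | 9.9% to 43.7% | 12% | no |

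The justification in Section 8.5 reproduces. At 90%, 9 and 6 are the smallest counts that satisfy it.

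**The same counts at the Synopsis level.** At 95% (a = 0.05), 9/19 gives 24.4% to 71.1% and 6/21 gives 11.3% to 52.2%. Both lower limits miss their benchmarks. The binomial tails agree: P(X ≥ 9 | n = 19, p = 0.25) = 0.0287 and P(X ≥ 6 | n = 21, p = 0.12) = 0.0328. Both lie between 0.025 and 0.05, so each count passes at 90% and fails at 95%.

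**What a 95% rule would require.** The smallest qualifying counts would be 10/19 (lower limit 28.9%) and 7/21 (14.6%). The chance of a high result would fall from 18.5% to 8.7% in SCLC at a true ORR of 35%, and from 23.1% to 10.9% in PAC at 20%. Neither document proposes these counts. The figures describe a different rule, not an effect of the discrepancy.

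**Who uses which level.** The Synopsis sentence governs how ORR is summarised. The cut-off rationale in Section 8.5 states its own level, 90%. The trigger is a count. Someone who followed the Synopsis literally would print a wider interval and still open the randomised phase at 9 or 6 responders.

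**The Simon test.** Success is also decided by counts: 11 of 44 and 5 of 41. Exact enumeration of the two-stage designs gives type I error 0.0481 and power 0.905 for SCLC, and 0.0457 and 0.902 for PAC, as planned. No interval enters. Nor does a 90% interval reproduce the test at its boundary: the lower limit is 14.7% at 11/44 (null 15%) and 4.9% at 5/41 (null 5%).

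**Actual size.** At 9/19 the interval width is 68.0 − 27.4 = 40.6 points at 90% and 71.1 − 24.4 = 46.7 at 95%, a difference of 6.1. At 6/21 the widths are 48.7 − 13.2 = 35.5 and 52.2 − 11.3 = 40.9, a difference of 5.4.

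**The case for a change.** The strongest argument for acting is that the contradiction needs no interpretation, concerns the primary endpoint and costs one figure to remove. Correcting it before results are known would leave a single prespecified interval. A one-sided 5% test also pairs naturally with a two-sided 90% interval, so the right value is not in doubt. At 95%, even 12/44, one responder above the success boundary, has a lower limit of 14.96%, just under the 15% null.

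The textual contradiction stands, and so does the arithmetic. The claimed consequences do not. The randomised-phase trigger cannot depend on the Synopsis, because the trigger is a count and its rationale specifies 90%. The pairing with the Simon test is only nominal, since the 90% limits at the design's own success boundaries also fall slightly below the nulls. The 12/44 figure therefore does not tell the two levels apart in the way suggested. The worry about choosing a level after the fact is met by SAP Section 7.5.1, which fixes 90% and names it the primary analysis.

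**Conclusion.** The Synopsis figure is a clerical slip, and the plan needs no change on this point. Protocol Sections 8.4.2.1 and 8.5 and SAP Section 7.5.1 agree on 90%, and the cut-offs satisfy their stated criterion at that level. An analyst working from the SAP will produce the 90% interval. The cut-offs, the choice of expansion design, the Simon error rates and power, and the sample sizes are the same whichever page is read. The most that is at stake is a descriptive interval wider by 6.1 points at 9/19 or 5.4 points at 6/21.

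This rests on two readings: that the counts are the operative trigger, as Table 3.1.2-1 and Section 8.5 state, and that the SAP governs the reported interval. If 95% had been intended throughout, Sections 8.4.2.1 and 8.5 and the SAP would all be wrong and the rationale for the cut-offs would have to be redone. Nothing in the documents points that way. The Synopsis can be aligned if the protocol is amended for another reason, but the slip does not warrant an amendment of its own.
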